#### 8. Study populations

#### 8.1. Patient flow

A CONSORT patient flow diagram will be drawn following the CONSORT 2010 standards (http://www.consort-statement.org/consort-2010).

#### 8.2. Definition of populations for analysis

#### 8.2.1. Full analysis set (FAS)

The full analysis set consists of all randomized patients fulfilling all inclusion criteria, regardless of whether they actually received the allocated monitoring or not or any subsequent protocol deviations during follow up visits. Patients will be analysed in the group they were randomized regardless of any cross-overs or loss to follow-up (intention-to-treat principle). This corresponds to the treatment-policy estimand.

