#### 8.2.2. Per-protocol (PP)

The per-protocol population consists of all subjects in the FAS who did not have any protocol deviations during follow up that could confound the interpretation of analyses conducted on the FAS. The following are common major protocol deviations:

- General protocol violations:
  - No hemodynamic instability at screening (i.e.  $MAP \ge 60 \text{ mmHg}$ )
  - No signs of hypoperfusion or organ dysfunction at screening (i.e. capillary refilling time < 3 seconds, urine output  $\geq$  0.5 ml/kg/h, lactate  $\leq$  2 mmol/l)
  - $\circ$   $\,$  Oesophageal conditions not allowing use of TEE, i.e.
    - Unrepaired tracheoesophageal fistula
    - Prior oesophageal or gastric surgery
    - Oesophageal obstruction or stricture
    - Oesophageal varices or diverticulum
    - Gastric or oesophageal bleeding
    - Recent oesophageal surgery
- Protocol violations in monitoring method:
  - Use of hTEE in conventional monitoring arms and vice versa
- Protocol violations in monitoring interval:
  - Mean interval among monitoring shorter than 6 h for the standard interval arms, and longer than 6 hours for the per-protocol interval arms.

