#### 9. Statistical analysis

#### 9.1. General

The primary analysis will be based on the FAS, analysing all patients in the treatment group they were randomized to. We will first test the primary hypothesis, the difference in time to hemodynamic stabilization between the hTEE and standard group. Second, we will evaluate the difference between the protocolled and standard monitoring. Differences in the primary outcome will be assessed using the Fine-Gray competing risk model accounting for the competing risk of death (Fine and Gray 1999).

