#### Primary analysis of primary endpoint

The analysis of the primary endpoint will be a superiority analysis based on the full analysis set, asking whether hTEE monitoring is superior in time to resolution of circulatory shock as compared to standard monitoring. We will use a Fine-Gray competing risk regression model accounting for the competing risk of death (Fine and Gray 1999), adjusted for the frequency of monitoring (protocolled vs standard).

The primary outcome will be censored after 6 days in the primary analysis, because continuous hTEE monitoring was only continued for 72h after randomisation. Patients which were discharged without reaching the primary endpoint before 6 days will be censored as well. The strength of the association between each covariate and the outcome is reflected by the sub-hazard ratio in these competing risks models. The sub-hazard ratio is the ratio of the hazard associated with the cumulative incidence function under different values of the covariate, taking into account the hazard of the competing event (death).

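### The full analysis set is labelled intention-to-treat but leaves out randomised patients who failed an inclusion criterion, and no efficacy analysis of all randomised patients is planned

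*SAP*

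**What the plan says.** Section 8.2.1 of the SAP gives the membership rule for the FAS: "The full analysis set consists of all randomized patients fulfilling all inclusion criteria". It then says what does not remove a patient: not receiving the allocated monitoring, and "any subsequent protocol deviations during follow up visits". On allocation it states "Patients will be analysed in the group they were randomized regardless of any cross-overs or loss to follow-up (intention-to-treat principle", and it equates the set with a treatment-policy estimand.

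Section 8.2.2 builds the PP set from the FAS: "The per-protocol population consists of all subjects in the FAS who did not have any protocol deviations during follow up". The list of major deviations that follows opens with "No hemodynamic instability at screening" and "No signs of hypoperfusion or organ dysfunction at screening". Oesophageal conditions, wrong monitoring method and wrong monitoring interval come after these.

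Section 9.1 makes the FAS the primary set: "The primary analysis will be based on the FAS, analysing all patients in the treatment group they were randomized to". Section 9.5.1 repeats that the primary endpoint analysis "will be a superiority analysis based on the full analysis set". Section 9.6 adds a PP analysis, FAS analyses with censoring at 3 and 28 days, and FAS subgroup analyses. The safety population in 8.2.3 is as-treated and, under 9.7, serves the safety analyses.

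**The concern.** An intention-to-treat set normally holds everyone randomised. Here a condition is added at the front of the definition, and none of the later wording takes it back. A patient found after randomisation to have missed an inclusion criterion leaves the primary analysis, and no planned efficacy analysis brings that patient back.

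The usual safeguard for such a filter is that it rests only on facts fixed before randomisation and is applied without knowledge of arm or outcome. The SAP does not say this. The trial is open-label and the statistician is unblinded (4.4). Section 4.3 describes randomisation in the past tense. The database has no built-in validation (7.1), so inconsistencies are found and queried at the cleaning stage (7.2). Eligibility could therefore be decided with allocation and outcome in view.

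The PP section adds doubt about what was intended, because it treats screening failures as a reason to leave the PP set, as though those patients were still in the FAS.

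**Working it through.** **Step 1: who is in the FAS.** Membership under 8.2.1 needs two things: being randomised and meeting all inclusion criteria. The tolerance clause covers (a) monitoring not received, (b) later deviations, (c) cross-over and (d) loss to follow-up. Failure of an inclusion criterion is none of these. The reference in 9.1 to all patients operates inside the FAS, so it does not widen the set.

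**Step 2: 8.2.1 beside 8.2.2.**

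| Item in the PP list | Present at | Fits the 'during follow up' wording? | Already out of the FAS under 8.2.1? |
|---|---|---|---|
| No hemodynamic instability | screening | no | yes, if it mirrors an inclusion criterion |
| No hypoperfusion or organ dysfunction | screening | no | yes, if it mirrors an inclusion criterion |
| Oesophageal conditions | not stated; reads as an exclusion criterion | unclear | no, because 8.2.1 names inclusion criteria only |
| Wrong method or interval | follow-up | yes | no |

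The third column needs no inference for the first two rows: a state at screening is not a deviation during follow-up. The fourth column does need one for those rows. It is supported by the target population in 3.1 (hemodynamically compromised patients), but the SAP does not list the criteria.

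**Step 3: which efficacy analyses use all randomised patients.** Primary: FAS. Section 9.6: PP, FAS, FAS. None uses all randomised patients.

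**Step 4: power.** Section 4.2 gives 458 patients for 80% power at two-sided 0.05. With a constant event proportion and no other loss, power at N patients is Φ(√(N/458) × 2.8016 − 1.96), where 2.8016 = 1.9600 + 0.8416. N = 458 returns Φ(0.8416) = 80%, the plan's own figure. Then:

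- N = 500: √1.0917 = 1.0449; Φ(0.967) = 83.3%
- N = 490 (2% excluded): Φ(0.938) = 82.6%
- N = 475 (5% excluded): Φ(0.893) = 81.4%

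**Step 5: type I error when exclusion follows eligibility.** The SAP gives no count of ineligible patients, so everything here is assumed: 250 per arm, exponential resolution times with median 18.5 h in both arms, censoring at 144 h (6 days), log-rank test at 0.05, no deaths, 20,000 trials per scenario (simulation error about 0.16 points). Twelve patients per arm are ineligible (12/250 = 4.8%), and their resolution hazard is two or four times that of the rest.

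| Excluded, one arm v the other | Hazard ×2 | Hazard ×4 |
|---|---|---|
| none | 4.9% | 4.8% |
| 12 v 12 (rule applied evenly) | 5.0% | 4.9% |
| 12 v 6 | 5.3% | 5.4% |
| 12 v 0 | 5.7% | 7.0% |

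If the exclusions are unrelated to outcome, 12 v 0 gives 5.2% (5.0% when 20% of patients are assumed to die before resolution). Even application does nothing to the error rate. Only wholly one-sided exclusion of patients who recover much faster moves it noticeably.

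**The case against.** The strongest reply is that 8.2.1 is the express and only definition of the FAS. Section 8.2.2 defines a subset, and a redundant entry in a list of common deviations does not override that definition. The inclusion criteria belong in the protocol, which is not at hand. If they are worded differently from the two short PP items, a patient could meet them and still be removed from the PP set, and there would be no overlap at all. Exclusion on screening facts, applied alike in both arms, leaves the comparison unbiased. Section 4.3 describes concealed allocation, section 1 says the SAP was set up before the final analysis, and the CONSORT diagram in 8.1 would show exclusions by arm.

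Most of this stands. A reader might infer that 8.2.1 and 8.2.2 flatly contradict each other and leave the primary set undefined. The documents do not support that, because 8.2.1 can be applied as written and the overlap is inferred. A reader might also infer that the primary result will be biased. Nothing in the SAP shows differential exclusion, and step 5 shows that even application is harmless.

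Three things survive. The intention-to-treat label is wider than the set it describes. The follow-up wording in 8.2.2 does not cover its own screening items. A CONSORT diagram gives counts, not the result with those patients included.

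**Conclusion.** The point holds as a defect of definition with low-to-moderate consequence. The primary set is narrower than its intention-to-treat label, the PP wording does not match its list, and no planned result would show whether leaving out ineligible patients mattered. That the first two PP items duplicate inclusion criteria is likely but not established by the SAP.

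The size is unknown because the number of ineligible patients is not given. Under the assumptions above, the power cost is under 2 points for up to 5% excluded (83.3% to 81.4%), and the type I error stays near 5% unless exclusion is strongly one-sided and linked to speed of recovery. The 7.0% figure is a what-if for that case, not an expected value. The case for changing the text rests on removing a decision that could be taken unblinded, not on a demonstrated error in the result.

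**What to change.** Preferred: in 8.2.1, define the FAS as all randomised patients, analysed in the group to which they were allocated. In 8.2.2, keep the screening violations as PP exclusions only, and describe the list as deviations 'at screening or during follow-up'.

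If the eligibility filter is kept: state that it uses only data recorded before randomisation, stop describing the filter as intention-to-treat, delete any PP items that duplicate inclusion criteria, and add to 9.6 a sensitivity analysis of the primary endpoint in all randomised patients.

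The cost is one sentence in each of 8.2.1 and 8.2.2 for the first option, or those edits plus one line in 9.6 for the second. The downside of an all-randomised FAS is slight dilution from any ineligible patients, which the planned PP analysis already addresses.

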#### 8.2.2. Per-protocol (PP)

The per-protocol population consists of all subjects in the FAS who did not have any protocol deviations during follow up that could confound the interpretation of analyses conducted on the FAS. The following are common major protocol deviations:

- General protocol violations:
  - No hemodynamic instability at screening (i.e.  $MAP \ge 60 \text{ mmHg}$ )
  - No signs of hypoperfusion or organ dysfunction at screening (i.e. capillary refilling time < 3 seconds, urine output  $\geq$  0.5 ml/kg/h, lactate  $\leq$  2 mmol/l)
  - $\circ$   $\,$  Oesophageal conditions not allowing use of TEE, i.e.
    - Unrepaired tracheoesophageal fistula
    - Prior oesophageal or gastric surgery
    - Oesophageal obstruction or stricture
    - Oesophageal varices or diverticulum
    - Gastric or oesophageal bleeding
    - Recent oesophageal surgery
- Protocol violations in monitoring method:
  - Use of hTEE in conventional monitoring arms and vice versa
- Protocol violations in monitoring interval:
  - Mean interval among monitoring shorter than 6 h for the standard interval arms, and longer than 6 hours for the per-protocol interval arms.

#### 8.2.3. Safety population

The safety population consists of all subjects that received a hTEE or a conventional monitoring and will be evaluated according to the intervention actually received.

CTU Bern	Statistical Analysis Plan ImaCorII	Date effective		
CTO Bern	Based on CS_STA_TEM-11_SAPtemplate_v01			Page 11 I 16

#### 8.3. Definition of sub-group populations in different analyses

Subgroups will be defined by the method (hTEE vs. standard monitoring) and the frequency (per protocol vs. standard interval) of hemodynamic monitoring.

#### 9. Statistical analysis

#### 9.1. General

The primary analysis will be based on the FAS, analysing all patients in the treatment group they were randomized to. We will first test the primary hypothesis, the difference in time to hemodynamic stabilization between the hTEE and standard group. Second, we will evaluate the difference between the protocolled and standard monitoring. Differences in the primary outcome will be assessed using the Fine-Gray competing risk model accounting for the competing risk of death (Fine and Gray 1999).

#### 9.2. Demographics and baseline characteristics

The patient characteristics of the FAS at baseline will be presented in a table, stratified by the four intervention arms (defined by both methods and both frequencies of hemodynamic monitoring), as number and percentage for categorical and mean and standard deviation for continuous variables. For data severely deviating from a normal distribution, we will present median and interquartile ranges. No statistical comparisons of patient characteristics at baseline will be performed. The following variables will be considered:

- Age
- Gender
- Weight
- Height
- Patient admission from: emergency department, ward, external ICU, coronary laboratory, op, and other
- Admission diagnosis: cardiovascular, gastrointestinal, metabolic, neurological, renal or genitourinary, respiratory, trauma, infectious
- Comorbidities: septic shock, chronic lung disease, chronic cardiovascular disease, chronic liver disease, chronic renal failure, immunosuppression, lymphoma, metastatic cancer, leukaemia or myeloma,
- Apache II score,
- SAPS II score, and
- SOFA score.

CTU Bern	Statistical Analysis Plan ImaCorII	Date effective: 2018-04-24		
	Based on CS_STA_TEM-11_SAPtemplate_v01			Page 12 I 16

UNIVERSITÄT BERN

#### 9.3. Procedural characteristics

Procedural characteristics will not be shown.

#### 9.4. Compliance to interventions

To validate compliance to the method of monitoring (only hTEE), we will descriptively present the duration of hTEE, and the number and percentage of early termination of hTEE monitoring. The frequency of hemodynamic monitoring will be validated by the time interval between examinations (based on date and time of examinations) and presented descriptively in each group.

#### 9.5. Primary analysis

The primary analysis will be based on the FAS. Since the primary outcome is a time to event outcome, no multiple imputation will be used.

#### 9.5.1. Primary comparison between hTEE and standard monitoring method

We will first test the primary hypothesis, the difference in time to resolution of circulatory shock between the hTEE monitoring and standard monitoring group (i.e. monitoring factor only).

#### Primary analysis of primary endpoint

The analysis of the primary endpoint will be a superiority analysis based on the full analysis set, asking whether hTEE monitoring is superior in time to resolution of circulatory shock as compared to standard monitoring. We will use a Fine-Gray competing risk regression model accounting for the competing risk of death (Fine and Gray 1999), adjusted for the frequency of monitoring (protocolled vs standard).

The primary outcome will be censored after 6 days in the primary analysis, because continuous hTEE monitoring was only continued for 72h after randomisation. Patients which were discharged without reaching the primary endpoint before 6 days will be censored as well. The strength of the association between each covariate and the outcome is reflected by the sub-hazard ratio in these competing risks models. The sub-hazard ratio is the ratio of the hazard associated with the cumulative incidence function under different values of the covariate, taking into account the hazard of the competing event (death).

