#### 4.2. Sample size

Sample size calculation is based on a retrospective analysis of a sample of 159 patients admitted to ICU of Inselspital Bern during a three-month period, which fulfilled the study entry criteria. Median time to resolution of hemodynamic instability as defined by discontinuation of vasopressors or inotropes in this sample was 18.5 hours. We used the Stata command artsurv to calculate the sample size (Barthel et al). We applied the unweighted logrank test and derived expected probabilities of hemodynamic stabilization and loss-to-follow up (i.e. death) over time from the retrospective analysis. To identify a clinically relevant reduction of time to resolution of hemodynamic instability of 25% (i.e. from 18.5 to 14.0 hours) we calculated a required sample size of 458 patients to achieve a power of 80% at a two-sided alpha level of 0.05 for the main effect (comparison of monitoring with/without hTEE). To account for an estimated drop-out rate of 10%, we choose a sample size of 125 patients for each of the four groups or 500 patients in total.

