#### 5. Hypothesis

The primary study hypothesis is that hemodynamic monitoring using hTEE in critically ill patients with hemodynamic compromise allows for an expedited reversal of circulatory impairment compared to standard ICU monitoring. The secondary hypothesis is that more frequent monitoring results in shorter reversal of hemodynamic shock as compared to standard monitoring.

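### The sub-hazard ratio, the only primary effect measure, mixes speed of shock resolution with mortality; no planned analysis separates them, though hypothesis, target and sample size concern speed

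*SAP*

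**What the plan says.** - **Hypothesis (SAP 5).** Monitoring with hTEE "allows for an expedited reversal of circulatory impairment compared to standard ICU monitoring". SAP 9.5.1 likewise asks whether hTEE is superior in time to resolution.
- **Target (SAP 4.2).** The effect to detect is a "clinically relevant reduction of time to resolution of hemodynamic instability of 25% (i.e. from 18.5 to 14.0 hours").
- **Sizing (SAP 4.2).** "We applied the unweighted logrank test and derived expected probabilities of hemodynamic stabilization and loss-to-follow up (i.e. death) over time". Death enters as loss to follow-up, which makes the sizing a cause-specific contrast. The stated result is "we calculated a required sample size of 458 patients", for 80% power at two-sided 5% on the hTEE main effect, raised to 500 for drop-out.
- **Primary model (SAP 9.5.1).** "We will use a Fine-Gray competing risk regression model accounting for the competing risk of death", adjusted for monitoring frequency, with censoring at 6 days. On the effect measure: "The strength of the association between each covariate and the outcome is reflected by the sub-hazard ratio in these competing risks models". The section adds that the SHR relates to the cumulative incidence function and takes the hazard of death into account.
- **Other analyses.** Time to death is a secondary outcome analysed by Cox regression (SAP 9.5.1). SAP 9.6 adds a per-protocol analysis, censoring at 3 and 28 days, and subgroups by method and frequency.
- **Change of model (SAP 10).** The competing-risk model is listed as a deviation from the protocol, made to account for death.

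**The concern.** In a Fine-Gray model, patients who die stay in the risk set for resolution. The SHR therefore depends on the share who ever resolve as well as on how fast patients resolve. With a median of 18.5 hours and a 144-hour horizon, almost every patient has resolved or died by the end, so the final share is governed by deaths before resolution.

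An SHR above 1 can thus come from faster resolution, fewer deaths or both, and nothing planned shows which. The contrast on which the trial was sized, a logrank comparison with death censored, is no longer estimated anywhere. Nor is any result planned in hours to set against the 4.5-hour target. At stake is whether a positive result may be worded as faster reversal, and whether a negative result rules out the planned gain in speed.

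**Working it through.** **1. The plan's own sample size.** The target gives a hazard ratio of 14.0/18.5 = 0.757 if times are exponential, that is 18.5/14.0 = 1.32 for the rate of resolution.
- Schoenfeld: 4 × (1.960 + 0.842)² / (ln 0.757)² = 4 × 7.849 / 0.0777 = 404.2, so 405 events.
- Freedman: 7.849 × (1.757/0.243)² = 409.4, so 410 events.
- Against 458 patients these imply event probabilities of 405/458 = 88.4% and 410/458 = 89.5%.

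The SAP does not print the event and death probabilities it used, so 458 can only be back-solved. It is plausible. About 12% of controls dying before resolution fits it.

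**2. Why the SHR moves.** Assume exponential hazards:
- resolution in controls: ln 2/18.5 = 0.03747 per hour;
- death in controls: 0.03747 × 0.12/0.88 = 0.00511 per hour, which gives 12% dying before resolution.

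With total hazard s and resolving share p, the cumulative incidence of resolution is F(t) = p(1 − e^(−st)), and the cumulative subdistribution hazard is −ln(1 − F).

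| Arm | s per hour | p | F(144 h) | −ln(1 − F) | Ratio to control | Hours to F = 50% |
|---|---|---|---|---|---|---|
| Control | 0.0426 | 0.880 | 0.878 | 2.104 | – | 19.7 |
| Speed 1.32, death hazard unchanged | 0.0546 | 0.906 | 0.906 | 2.365 | 1.12 | 14.7 |
| Speed 1.00, death hazard ratio 0.67 | 0.0409 | 0.916 | 0.914 | 2.450 | 1.16 | 19.3 |

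In the second row the ratio starts at 1.32 in the first hours and falls to 1.12 by 144 hours. In the third row it starts at 1.00 and rises to 1.16. The fitted SHR averages over this path. The time to 50% resolved separates the two cases clearly: a gain of 5.0 hours against 0.4 hours.

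**3. Simulation.** The same hazards were used, with 250 patients per arm (500 in total), a 144-hour horizon, no other censoring and no frequency effect. There were 3,000 trials per scenario, and SHRs came from 400,000 simulated patients. In the last two columns, a win is a result significant at two-sided 5% in favour of hTEE (nominal 2.5% under no effect).

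| Scenario | Control deaths before resolution | SHR | Fine-Gray wins | Cause-specific wins |
|---|---|---|---|---|
| Speed 1.32, death hazard unchanged | 5% | 1.26 | 71% | 86% |
| | 12% | 1.23 | 61% | 83.5% |
| | 20% | 1.23 | 53% | 79% |
| | 30% | 1.23 | 48.5% | 75% |
| No speed effect, death hazard ratio 0.67 | 5% | 1.04 | 7% | 2% |
| | 12% | 1.08 | 13.5% | 2% |
| | 20% | 1.12 | 21% | 2% |
| | 30% | 1.17 | 31% | 3% |
| No effect on either hazard | 5–30% | 1.00 | 2–3% | 2–3% |

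The Monte Carlo standard error at 12% deaths is 0.9 points for the 61% and 0.6 points for the 13.5%, hence about 60% and about 12 to 14%. The cause-specific power of about 83% with 500 patients agrees with the plan's 80% with 458.

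**The case against.** **The model is legitimate, and this stands.** Fine-Gray measures the total effect on the cumulative incidence of resolution. Fewer deaths do mean more patients resolved by any given hour. SAP 9.5.1 says openly that the SHR takes death into account, and SAP 10 records the change. A reader might infer that the test is invalid. It is not: with neither hazard affected, its two-sided error was 4 to 7% in the simulation, close to nominal. If hTEE speeds resolution and also cuts the death hazard to 0.67, Fine-Gray has slightly more power than the cause-specific test (87% against 84% at 12% deaths).

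**Extreme cases should not carry the point, and this stands.** A reader might infer that a false claim of speed is likely in most trials. With no speed effect, a rate of about 55% needs 20% against 10% dying before resolution, a death hazard ratio of (0.10/0.90)/(0.20/0.80) = 0.44. Nothing in the SAP supports that for a monitoring device. Likewise, 15% dying in both arms with a speed ratio of 1.32 is not neutral on mortality, because the hTEE death hazard must then also rise by 1.32. And 12% against 18% implies a death hazard ratio of 1.32 × (0.18/0.82)/(0.12/0.88) = 2.1.

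**The Cox model for death is a safeguard, and this stands in part.** It would usually expose a large mortality difference. It does not estimate the speed of resolution, is not tied to the primary conclusion, and cannot help where the death hazard is unchanged.

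**The cause-specific hazard ratio is not a pure measure of speed, and this stands.** It conditions on being alive and still in shock. If hTEE keeps sicker patients alive, it is subject to selection. The simulation avoids this by assuming homogeneous patients. Nor does any hazard ratio convert to hours without a curve shape, which is why a direct contrast in hours is worth adding.

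**Conclusion.** The point holds as a mismatch between question and measure. The hypothesis, target and sizing are about speed, the only primary measure combines speed with mortality, and no companion analysis separates them. Two consequences follow at 12% control deaths:

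- The planned speed effect with an unchanged death hazard appears as an SHR of about 1.23 with about 60% power, against about 83% for a cause-specific analysis. This loss needs no effect on the death hazard.
- With no speed effect, a death hazard ratio of 0.67 gives a result favouring hTEE in about 12 to 14% of trials instead of 2.5%. This needs a real mortality difference, and at 5% deaths it falls to about 7%.

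These sizes rest on exponential hazards, no discharge censoring and an assumed mortality. Other inputs shift the values, but not the fact that the SHR depends on both hazards. The documents do not show that 458 is wrong or that Fine-Gray must be abandoned.

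**What to change.** Keep Fine-Gray as the primary test in SAP 9.5.1. Prespecify as supportive output, for the same population, covariates and 6-day horizon:

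1. A cause-specific Cox model for resolution, with death censored at the time derived in SAP 7.3, and one for death before resolution, both reported beside the SHR.
2. Cumulative incidence curves for resolution and death by arm, with the time to 50% resolved in hours and its difference with a 95% confidence interval.

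Add a statement that the SHR is described as an effect on the cumulative incidence of resolution, and that speed is read from the cause-specific hazard ratio, which conditions on being alive and still in shock.

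Do not add a new decision gate on the primary claim. Requiring the two ratios to agree would need a definition of agreement. It could also only remove claims, so it could not recover a speed effect that Fine-Gray misses.

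The cost is SAP wording, two extra models on times already derived, and a more cautious headline. SAP 1 places the plan before the final analysis, so this can still be prespecified.
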